
Planned Sample Size:
	
A total of 3300 subjects are planned to be enrolled:
 
 
• Group 1: MenACYW conjugate vaccine (Lot 1): planned = 900 (evaluable = 810) 
 
• Group 1a: 400 subjects 10 to 17 years of age
 
• Group 1b: 500 subjects 18 to 55 years of age
 
 
 
• Group 2: MenACYW conjugate vaccine (Lot 2): planned = 900 (evaluable = 810) 
 
• Group 2a: 400 subjects 10 to 17 years of age
 
• Group 2b: 500 subjects 18 to 55 years of age
 
 
 
• Group 3: MenACYW conjugate vaccine (Lot 3): planned = 900 (evaluable = 810) 
 
• Group 3a: 400 subjects 10 to 17 years of age
 
• Group 3b: 500 subjects 18 to 55 years of age
 
 
 
• Group 4: Menactra®: planned = 600 (evaluable = 540) 
 
• Group 4a: 300 subjects 10 to 17 years of age
 
• Group 4b: 300 subjects 18 to 55 years of age
 
 
 
 
The planned number of subjects is based on a 10% dropout rate allowing around 88% power to reject the primary hypotheses simultaneously assuming the independence between each of the endpoints.

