3.1 Trial Design

This is a Phase III, modified double-blind, randomized, parallel-group, active-controlled, multi-center study to evaluate immune lot consistency of MenACYW conjugate vaccine, evaluate the immune non-inferiority versus Menactra[®], and describe the safety and additional immunogenicity of these study vaccines in adolescents and adults aged 10 to 55 years in the United States.

Healthy, meningococcal-vaccine naïve adolescents and adults will be randomized in a 3:3:3:2 ratio to the following groups:

- Group 1: MenACYW conjugate vaccine (Lot 1)
 - Group 1a: 400 subjects 10 to 17 years of age
 - Group 1b: 500 subjects 18 to 55 years of age
- Group 2: MenACYW conjugate vaccine (Lot 2)
 - Group 2a: 400 subjects 10 to 17 years of age
 - Group 2b: 500 subjects 18 to 55 years of age
- Group 3: MenACYW conjugate vaccine (Lot 3)
 - Group 3a: 400 subjects 10 to 17 years of age
 - Group 3b: 500 subjects 18 to 55 years of age
- Group 4: Menactra[®]
 - Group 4a: 300 subjects 10 to 17 years of age
 - Group 4b: 300 subjects 18 to 55 years of age

All subjects will provide blood samples for immunogenicity assessment at baseline (pre-vaccination) and at 30 to 44 days post-vaccination.

Solicited adverse event (AE) information will be collected for 7 days after vaccination, unsolicited AE information will be collected from Visit 1 (Day [D] 0) to Visit 2 (D30 [+14 days]), and serious adverse event (SAE) information will be collected from D0 through D180 (+14 days) after vaccination.

Medically-attended adverse events (MAAEs) information will be collected throughout the study from Visit 1 to Visit 2 (as part of the collection of unsolicited AE information) and from Visit 2 through D180 (+14 days) (as MAAEs).

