5.1.2.4.1 Hypothesis

No hypotheses will be tested. Descriptive statistics will be presented.

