5.1.2.4.2 Statistical Methods

The ratio of GMTs of meningococcal serogroups A, C, Y, and W between the MenACYW conjugate vaccine Groups 1- 3 pooled (Lots 1, 2, and 3 combined) and the Menactra[®] Group 4 30 days after the administration of vaccine will be calculated and 95% CI will be provided.

Assuming that \log_{10} transformation of the data follows a normal distribution, the \log_{10} (data) will be used for the statistical analysis, then antilog transformations will be applied to the results of calculations, in order to provide the results in terms of GMTs.

For each of the GMT ratios, the statistical methodology will be based on the use of the 2-sided 95% CI of difference in means of post-vaccination \log_{10} transformed titers between the 2 groups with normal approximation.

The 95% CI for the difference in $\log_{10}(\text{GMT})$ between Group 1-3 pooled (Lots 1, 2, and 3 combined) and Group 4 will be in the form:

$$\bar{X}_{123} - \bar{X}_4 \pm t(1 - \alpha/2, n_{123} + n_4 - 2) \cdot S \sqrt{1/n_{123} + 1/n_4}$$

where $\bar{X}_i = \log_{10}(\text{GMT})$ is the mean of $\log_{10}(\text{titer})$ of Group i ,

$S^2 = [(n_{123} - 1) S_{123}^2 + (n_4 - 1) S_4^2] / (n_{123} + n_4 - 2)$ is the pooled sample variance,

n_i and S_i^2 are the sample size and sample variance of Group i ,

$t(1 - \alpha/2, n_{123} + n_4 - 2)$ is the $100(1 - \alpha/2)$ percentile of the t -distribution with degrees of freedom $df = n_{123} + n_4 - 2$.

The 95% CI for the ratio of GMTs can be obtained by taking antilog transformations for the calculated 95% CI for the difference in $\log_{10}(\text{GMT})$.

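### The pooled-variance interval for the MenACYW/Menactra GMT ratio (about 2430 versus 540 subjects) has its nominal 95% coverage only if the two vaccines' titer variances are equal

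*SAP*

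**What the plan says.** SAP 5.1.2.4.2 covers the hSBA GMT ratio of the three pooled MenACYW lots to Menactra. It says that "the statistical methodology will be based on the use of the 2-sided 95% CI of difference in means" on the log10 scale, then fixes the formula. The interval for the difference "between Group 1-3 pooled (Lots 1, 2, and 3 combined) and Group 4 will be in the form" of a t interval whose standard error is S times the square root of 1/n123 + 1/n4, on n123 + n4 − 2 degrees of freedom. S² combines the variances of both vaccine groups and "is the pooled sample variance".

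The group sizes are very unequal. SAP 3.1 has subjects "randomized in a 3:3:3:2 ratio", so the pooled lots outnumber Menactra 9 to 2. The Protocol Synopsis gives each lot "planned = 900 (evaluable = 810") and Menactra "planned = 600 (evaluable = 540"), and adds: "The planned number of subjects is based on a 10% dropout rate".

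SAP 5.1.2.4.1 sets the status of the comparison: "No hypotheses will be tested. Descriptive statistics will be presented". Protocol 12.1.2.4 asks for the same two-sided 95% interval with a normal approximation but names no variance estimator. In their readable text, neither document states or justifies equal variances for the two vaccines, and neither plans an unequal-variance alternative.

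**The concern.** With unequal group sizes, a pooled-variance standard error is right only when the two variances are equal. Here the weights run almost exactly the wrong way round. MenACYW supplies about 82% of the weight in S², whereas under equal variances about 82% of the sampling variance of the difference comes from Menactra. If the two spreads differ, the estimate is taken mostly from the group that matters less.

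The documents give reasons to treat equal variance as an assumption needing support:

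- The vaccines differ in carrier and in polysaccharide content (Protocol 6.1.1.1 and 6.1.2.1).
- Titers below the LLOQ are set to half of it, and titers at or above the ULOQ are set to the ULOQ (SAP 4.4.2.1). This compresses the two distributions differently if they sit at different levels.
- The planned age mix differs slightly: 400/900 = 44% adolescents per lot and 300/600 = 50% in the Menactra group.

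None of these shows that the variances do differ, or which would be larger.

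At stake is the accuracy of the 95% label on the only between-vaccine hSBA GMT ratio in the plan. It is reported for four serogroups and repeated on PPAS2 and FAS2 (SAP 5.1.4).

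**Working it through.** **Inputs from the documents.** 900 planned per lot, 600 planned for Menactra, 10% dropout (Protocol Synopsis); pooled-variance t interval (SAP 5.1.2.4.2).

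**Plan's own figures.** 900 × 0.9 = 810 and 3 × 810 = 2430; 600 × 0.9 = 540. The stated evaluable numbers are reproduced, and 2430/540 = 4.5.

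**Assumption.** No SD of log10 titer by vaccine can be read in either document (the power sections are redacted). I assume a MenACYW SD of 0.6 and a Menactra/MenACYW SD ratio r from 0.8 to 1.5. The standard-error ratio and the coverage depend only on r; the 0.6 matters only for absolute widths.

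**Weights.** MenACYW share of S²: 2429/2968 = 82%. Menactra share of the variance of the difference under equal variances: (1/540)/(1/540 + 1/2430) = 82%.

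**Formulas.**

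- SE in the SAP: S × √(1/2430 + 1/540), with S² = (2429·s₁² + 539·s₄²)/2968
- True SE: √(s₁²/2430 + s₄²/540)
- Actual coverage: 2Φ(t × SE_SAP/SE_true) − 1, with t ≈ 1.961

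**One case in full, r = 1.25 (0.60 versus 0.75).**

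- S² = (2429 × 0.36 + 539 × 0.5625)/2968 = 0.3968, so S = 0.630
- SE_SAP = 0.630 × 0.0476 = 0.0300
- SE_true = √(0.36/2430 + 0.5625/540) = 0.0345
- Ratio = 0.869; coverage = 2Φ(1.961 × 0.869) − 1 ≈ 91.1%
- Half-width factors: pooled 10^0.0588 = 1.145; unequal-variance 10^0.0677 = 1.169 (Satterthwaite df about 700)

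**Range.**

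| SD ratio Menactra/MenACYW | SE_SAP / SE_true | Actual coverage | Half-width factor, pooled | Half-width factor, unequal-variance |
|---|---|---|---|---|
| 0.8 | 1.151 | 97.6% | 1.133 | 1.114 |
| 0.9 | 1.069 | 96.4% | 1.135 | 1.126 |
| 1.0 | 1.000 | 95.0% | 1.1375 | 1.1377 |
| 1.1 | 0.941 | 93.5% | 1.140 | 1.150 |
| 1.25 | 0.869 | 91.1% | 1.145 | 1.169 |
| 1.5 | 0.779 | 87.3% | 1.153 | 1.202 |

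A simulation with 40,000 replicates gave pooled-interval coverage of 97.6%, 91.1% and 87.4% at ratios 0.8, 1.25 and 1.5. The unequal-variance interval stayed at 95.0% to 95.2%.

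**In terms of a reported ratio.** For an illustrative GMT ratio of 2.0 at r = 1.25, the SAP interval would run from 2/1.145 = 1.75 to 2 × 1.145 = 2.29. The unequal-variance interval would run from 2/1.169 = 1.71 to 2 × 1.169 = 2.34.

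**Lot-to-lot comparison.** At 810 versus 810 the pooled and unequal-variance standard errors are identical at every SD ratio tried (0.8, 1.25, 1.5). SAP 5.1.1.1.2 is unaffected at the planned sizes.

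**The case against.** The strongest reply is that nothing in the trial turns on this interval. Secondary Objective 4 has no hypothesis, margin or success rule, and the formal between-vaccine claims rest on seroresponse with Wilson-score intervals (SAP 5.1.1.2.2 and the secondary objectives that refer to it). The pooled t interval on log titers is conventional, is explicitly pre-specified and matches the form used for the lots. The SDs are assumed; a 10% difference moves coverage by only about 1.5 points, and if Menactra titers are less spread the interval is merely conservative. Unequal spread would also be visible to readers: SAP Table 5.1 has the log10 mean and SD reported, and the single-group GMT intervals in SAP Section 5 use each group's own variance.

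All of that stands as a limit on importance. It does not make the stated coverage unconditional. Because the objective is descriptive, the interval is its main inferential output, and a reader should not have to combine three lots and recompute it. Convention is weaker support here than for the lots, where equal planned sizes make the choice of estimator immaterial.

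A reader might infer that the reported intervals will miss 95% coverage. The documents do not support that: no SDs by vaccine are visible, the redacted sections may contain relevant assumptions, and with equal variances coverage is nominal. A reader might also infer that lot consistency or non-inferiority is compromised. Neither is, since the lots are balanced by design and the seroresponse intervals do not use a pooled variance.

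**Conclusion.** The point holds as a conditional one and is minor. At about 2430 versus 540, the interval in SAP 5.1.2.4.2 has its stated coverage only under equal variances, which the readable text neither states nor supports. For assumed SD ratios from 0.8 to 1.5, coverage runs from about 97.6% down to about 87.3%; within 10% of equality it stays between about 93.5% and 96.4%. Direction and actual size cannot be determined from the documents. The sample sizes are planned evaluable numbers; actual per-protocol counts may differ, but an imbalance near 4.5:1 would remain. The consequence is confined to how accurately the uncertainty around a descriptive GMT ratio is reported.

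**What to change.** In SAP 5.1.2.4.2, replace the pooled form with the unequual-variance (Welch) interval: standard error √(S₁₂₃²/n₁₂₃ + S₄²/n₄), with Satterthwaite degrees of freedom. Apply it also to the PPAS2 and FAS2 repeats in SAP 5.1.4. Leave SAP 5.1.1.1.2 as it is.

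The cost is one formula. Protocol 12.1.2.4 names no variance estimator, so the change can be confined to the SAP. When the SDs are equal, essentially no precision is lost at these sizes.

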5.1.3 Statistical Methods for Observational Objectives

5.1.3.1 Hypothesis

No hypotheses will be tested. Descriptive statistics will be presented.

5.1.3.2 Statistical Methods

5.1.3.2.1 Immunogenicity

Descriptive statistics will be provided for the antibody titers against meningococcal serogroups contained in each lot of MenACYW conjugate vaccine and in Menactra[®].

In general, categorical variables will be summarized and presented by frequency counts, percentages, and CIs. The 95% CIs of point estimates will be calculated using the normal approximation for quantitative data and the exact binomial distribution (Clopper-Pearson method) for percentages (7). For GMTs, 95% CIs of point estimates will be calculated using normal approximation assuming they are log-normally distributed. RCDC figures will be provided for the antibody titers against meningococcal serogroups.

In summary, descriptive analyses on A, C, Y, and W serogroups will include but not be limited to:

- hSBA GMTs and 95% CI at each time point for each group
- hSBA titer distribution and RCDC

- Proportion of subjects with hSBA titer $\geq 1:4$ and $\geq 1:8$ and 95% CI at D0 and D30 for each group
- Proportion of subjects with hSBA titer ≥ 4 -fold rise from pre-vaccination to post-vaccination, and 95% CI
- rSBA GMTs and 95% CI at each time point in a subset of 100 subjects in each group
- rSBA titer distribution and RCDC
- Proportion of subjects with rSBA titer $\geq 1:8$ and $\geq 1:128$ and 95% CI at D0 and D30 in a subset of 100 subjects in each group
- Proportion of subjects with rSBA titer ≥ 4 -fold rise from pre-vaccination to post-vaccination and 95% CI
- Vaccine seroresponse (as defined in Section 4.4.2.4) against meningococcal serogroups A, C, Y, and W measured by rSBA and 95% CI

5.1.3.2.2 Safety

Safety results in Section 4.3.2.2 will be described for subjects in all study groups. The main parameters for the safety endpoints will be described by 95% CIs (Clopper-Pearson method) (7). Analyses will contain at least the descriptions listed in Table 5.2:

Table 5.2: Statistical analyses for safety observational objective

Safety Events	Time and Group	Description
Immediate unsolicited systemic AE	Within 30 minutes after injection for all subjects in Groups 1 - 4 at D0	Proportion of subjects that have the event, MedDRA terms, intensity, relationship to vaccine, study discontinuation, duration
Solicited injection site reactions	Up to 7 days after D0 for all subjects in Groups 1 - 4	Proportion of subjects that have the event, time of onset, duration, intensity, action taken, study discontinuation, number of days of occurrence, temperature collection routes
Solicited systemic reactions	Up to 7 days after D0 for all subjects in Groups 1 - 4	
Unsolicited AE	Up to 30 days after D0 for all subjects in Groups 1 - 4	Proportion of subjects that have the event, MedDRA terms, time of onset, duration, intensity, relationship, action taken, study discontinuation
SAE	Up to 6-month follow-up after D0 for all subjects in Groups 1 - 4	Proportion of subjects that have the event, MedDRA terms, time of onset, duration, relationship, seriousness criteria, outcome, study discontinuation
MAAE	Between Visit 1 and Visit 2 for all subjects in Groups 1 - 4 (as unsolicited AE) From Visit 2 to 6-month follow-	Proportion of subjects that have the event, MedDRA terms, time of onset, duration, intensity, relationship, action taken, outcome, study discontinuation

	up contact for all subjects in Groups 1 - 4	
--	---	--

5.1.4 Complementary Output

Additional analyses by age group, gender, and racial origin will be provided in Appendix 15 of the CSR.

Immunogenicity analyses:

- hSBA GMTs and 95% CI at each time point for each group – Per-Protocol Analysis Set
- Vaccine seroresponse against meningococcal serogroups A, C, Y, and W measured by hSBA and 95% CI – Per-Protocol Analysis Set
- rSBA GMTs and 95% CI at each time point for each group – Per-Protocol Analysis Set
- Vaccine seroresponse against meningococcal serogroups A, C, Y, and W measured by rSBA and 95% CI – Per-Protocol Analysis Set

Safety analyses:

- Safety overview after injection –Safety Analysis Set

Additional analyses will also be performed on SafAS2 with the following analyses:

- Safety overview after injection - Safety Analysis Set 2
- Unsolicited non-serious AEs in the six subjects at site [REDACTED] excluded from the Safety Analysis Set
- Solicited reactions in the six subjects at site [REDACTED] excluded from the Safety Analysis Set

Additional analyses will also be performed on PPAS2 and FAS2 with the following analyses:

- Equivalence of hSBA GMT against meningococcal serogroups A, C, Y, and W among 3 lots (Groups 1-3) 30 days after vaccination
- Non-inferiority of hSBA vaccine seroresponse rate for MenACYW conjugate vaccine (Groups 1-3 pooled) versus Menactra® (Group 4)
- Non-inferiority of hSBA vaccine seroresponse rate for MenACYW conjugate vaccine (Groups 1b-3b pooled) versus Menactra® (Group 4b)
- Non-inferiority of hSBA vaccine seroresponse rate for MenACYW conjugate vaccine (Groups 1a-3a pooled) versus Menactra® (Group 4a)
- Difference of hSBA vaccine seroresponse rate against meningococcal serogroups A, C, Y, and W among 3 lots (Groups 1-3)
- Comparison of the hSBA GMT for MenACYW conjugate vaccine (Groups 1-3 pooled) versus Menactra® (Group 4)

5.2 Analysis Sets

Four analysis sets will be used: the Full Analysis Set (FAS), the Per-Protocol Analysis Set (PPAS), the Safety Analysis Set (SafAS), and the rSBA subset.

During the conduct of the study and before database lock, additional analyses sets (PPAS2, FAS2 and SafAS2) are added as needed and are detailed in each section.

5.2.1 Full Analysis Set

The FAS is defined as the subset of subjects who received at least one dose of the study vaccine and had a valid post-vaccination blood sample result, i.e. a result different from not reportable (NR) or missing for at least one serogroup. All subjects will be analyzed according to the treatment group to which they were randomized.

Through data review and further investigation, it was found that at site [REDACTED] BL2 sample labels had been affixed to the sera samples collected during Visit 1, and BL1 labels were affixed to the Visit 2 sera sample. All 18 subjects from this site were incorrectly labeled and the investigation saw no other similar issues at other sites. Due to the mislabeling of sera samples at site [REDACTED], FAS2 will be defined the same as FAS but excluding all subjects from site [REDACTED].

5.2.2 Safety Analysis Set

The SafAS is defined as those subjects who have received at least one dose of the study vaccine and have any safety data available. All subjects will have their safety analyzed according to the vaccine they actually received.

If the vaccine received by a subject does not correspond to any study group, the subject will be excluded from the SafAS. The corresponding safety data will be presented in separate listings.

Due to the GCP quality issue related to safety data for six subjects [REDACTED], the safety data of these six subjects are regarded as not reliable, and they are excluded from the SafAS.

SafAS2 is defined the same as SafAS, but with adding those six subjects back into the safety analysis set.

5.2.3 Per-Protocol Analysis Set

The PPAS is a subset of the FAS. The subjects presenting with at least one of the following relevant protocol deviations will be excluded from the PPAS:

- Subject did not meet all protocol-specified inclusion criteria or met at least one of the protocol-specified exclusion criteria
- Subject did not receive vaccine
- Subject received a vaccine other than the one that he / she was randomized to receive

- Preparation and / or administration of vaccine was not done as per-protocol
- Subject did not receive vaccine in the proper time window (Visit 1, which is Day 0)
- Subject did not provide post-dose serology sample in the proper time window (Visit 2, which is 30 to 44 days after the vaccination at Visit 1) or a post-dose serology sample was not drawn
- Subject received a protocol-prohibited Category 2 or Category 3 therapy / medication / vaccine
- Subject's serology sample did not produce a valid test result, i.e. a result different from 'NR' or missing for at least one serogroup (either pre or post-vaccination)
- Subject had other protocol violations that affected the subject's immune response, as determined by the clinical team before locking the database.

Through data review and further investigation, it was found that at site [REDACTED], BL2 sample labels had been affixed to the sera samples collected during Visit 1, and BL1 labels were affixed to the Visit 2 sera sample. All 18 subjects from this site were incorrectly labeled and the investigation saw no other similar issues at other sites. Due to the mislabeling of sera samples at site [REDACTED], PPAS2 will be defined the same as PPAS but excluding all subjects from site [REDACTED] for the purpose of additional sensitivity analyses.

5.2.4 Other Analysis Set

rSBA subset

The rSBA subset is defined as those subjects who received the vaccine as per randomization and provided a valid post-vaccination rSBA result.

5.2.5 Populations Used in Analyses

The primary immunogenicity analyses will be performed on the PPAS, and will be confirmed on the FAS. In the FAS, subjects will be analyzed by the vaccine group to which they were randomized.

All safety analyses will be performed on the SafAS. Subjects will be analyzed according to the vaccine they actually received.

5.3 Handling of Missing Data and Outliers

5.3.1 Safety

No replacement will be done. In all subject listings, partial and missing data will be clearly indicated as missing.

5.3.1.1 Immediate

For unsolicited non-serious systemic AEs, a missing response to the "Immediate" field is assumed to have occurred after the 30-minute surveillance period and will not be imputed.

For SAEs, missing or partially missing elapsed time from last vaccination recorded if within 24 hours will be assumed to have occurred after the 30-minute surveillance period and will not be imputed. Such SAEs will not be considered as immediate.

5.3.1.2 Causality

Missing causality (relationship) for unsolicited non-serious AEs and SAEs will be considered at the time of analysis as related to vaccination.

5.3.1.3 Measurements

Partially missing temperatures will be handled as described in Section 4.4.1.1.1.

5.3.1.4 Intensity

For solicited reactions, missing intensities will be handled as described in Section 4.4.1.1.1. For unsolicited non-serious AEs, missing intensities will remain missing and will not be imputed.

5.3.1.5 Start Date and Stop Date

Missing or partially missing start dates for unsolicited AEs will remain missing and not be imputed. If the start date is missing or partially missing, the time of onset will be considered to be missing. Nevertheless unsolicited AEs with missing time of onset will be included in analyses according to the visit collected.

Missing or partially missing stop dates for AEs (solicited reactions and unsolicited AEs) will remain missing and not be imputed.

5.3.2 Immunogenicity

Missing data will not be imputed. No test or search for outliers will be performed.

LLOQ and ULOQ management will be performed as described in Section 4.4.2.1.

The derived endpoint of fold-rise is computed for extreme values, to minimize the numerator and maximizes the denominator as in Section 4.4.2.3.

5.3.3 Efficacy

Not applicable.

5.4 Interim / Preliminary Analysis

No interim / preliminary analyses are planned.

5.5 Determination of Sample Size and Power Calculation

5.5.1 Calculation of Sample Size

[REDACTED]

